5.4 Potential Serious Hepatotoxicity

For a subject who experiences an elevation in aspartate aminotransferase (AST) or alanine aminotransferase (ALT) that is ≥ 3 times the upper limit of normal (ULN), the total bilirubin level should also be evaluated. If the total bilirubin is ≥ 2 times the ULN, complete an IRE form with all values listed and also record it as an AE in the CRF.

5.5 Pregnancy

Women of childbearing potential (WOCBP) are women whose menstruation has started and who are not documented as sterile (ie, who have had a bilateral oophorectomy or hysterectomy, or who have been in the menopause for at least 12 months).

For each male subject who is sexually active with WOCBP, there must be a documented agreement that the subject and his partner will take effective measures (ie, 2 different approved methods of birth control) to prevent pregnancy during the course of the trial and for at least 30 days after the last dose of IMP. Unless the subject or his partner is sterile (ie, women who have had a bilateral oophorectomy, have had a hysterectomy, or have been in the menopause for at least 12 consecutive months; or men who have had a bilateral orchidectomy) or agrees to remain abstinent during the trial and for 30 days after the last dose of IMP, 2 of the following approved methods of birth control must be used: vasectomy, tubal ligation, intrauterine device, birth control pills, condom with spermicide, or occlusive cap (vaginal diaphragm or cervical/vault cap) with spermicide. Any single method of birth control, including vasectomy and tubal ligation, may fail, leading to pregnancy. The contraceptive methods will be documented in the CRF. Male subjects must also agree not to donate sperm from trial screening until 30 days have elapsed after the last dose of IMP.

Before enrolling subjects in this clinical trial, the investigator or subinvestigator must review the information below about trial participation as part of the consent obtaining process. The topics should generally include:

- General information
- Informed consent form
- Pregnancy prevention information
- Drug interactions with hormonal contraceptives
- Contraceptives in current use
- Follow-up of a reported pregnancy

Before trial enrollment, men and WOCBP must be advised of the importance of avoiding pregnancy during trial participation and the potential risks associated with an unintentional pregnancy. Subjects must sign the ICF confirming that the above-mentioned risks and the consequences were discussed.

Subjects will be instructed to contact the investigator or subinvestigator immediately if their partners suspect that they might be pregnant (eg, missed or late menstrual cycle) during the trial.

The investigator or subinvestigator must immediately notify the sponsor of any pregnancy in a subject's partner associated with IMP exposure during the trial and until 30 days after the last dose of IMP, and record the event in the IRE form and forward it to the sponsor. The sponsor will forward the Pregnancy Surveillance Form(s) to the investigator or subinvestigator to monitor the outcome of the pregnancy.

Protocol-required procedures for follow-up must be performed. Other appropriate pregnancy follow-up procedures should be considered if indicated. In addition, the investigator or subinvestigator must report to the sponsor, using the Pregnancy Surveillance Form(s), follow-up information regarding the course of the pregnancy, including perinatal and neonatal outcome. Infants will be followed for a minimum of 6 months from the date of birth.

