3.7.3.10 Post-treatment Follow-up

Subjects will visit the trial site at any date and time that is convenient to them between 6 and 8 days after the final IMP administration and undergo the following examinations/assessments. Subjects who are withdrawn from the IMP administration for any reason will also undergo the following examinations/assessments between 6 and 8 days after withdrawal.

- Clinical laboratory tests (hematology, biochemistry, and urinalysis)
- Physical examination
- Vital signs (blood pressure, pulse rate, and body temperature)
- Body weight
- ECG (12-lead ECG)
- AEs
- Concomitant medications/therapies

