3.7.9 End of Trial

The end of trial date is defined as the end date of post-treatment follow-up. If the subject is lost to follow up, it will be the date of the final contact attempt.

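### Protocol 5.5 limits the subject's instruction to report a suspected partner pregnancy to the trial itself, while its contraception, sperm-donation and sponsor-notification windows run to 30 days after the last dose

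*Protocol*

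**What the plan says.** Protocol 5.5 contains four time limits relating to partner pregnancy.

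- **Contraception:** the subject and his partner take measures "to prevent pregnancy during the course of the trial and for at least 30 days after the last dose of IMP".
- **Sperm donation:** subjects must "agree not to donate sperm from trial screening until 30 days have elapsed after the last dose of IMP".
- **Sponsor notification:** the investigator must notify the sponsor at once of a partner pregnancy "associated with IMP exposure during the trial and until 30 days after the last dose of IMP". Infants are then followed for at least 6 months from birth.
- **Subject's own report:** subjects are told to get in touch with the site "immediately if their partners suspect that they might be pregnant (eg, missed or late menstrual cycle) during the trial".

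The first three limits run to 30 days after the last dose. The fourth mentions only the trial.

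Protocol 3.7.9 fixes where the trial ends: "The end of trial date is defined as the end date of post-treatment follow-up". For a subject lost to follow-up, "it will be the date of the final contact attempt". Protocol 3.7.3.10 places the follow-up visit "between 6 and 8 days after the final IMP administration". Subjects withdrawn from dosing "will also undergo the following examinations/assessments between 6 and 8 days after withdrawal". The schedule in Table 3.7-1 has nothing after that visit.

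**The concern.** A partner pregnancy is an immediately reportable event (Protocol 5.1). The sponsor chose a 30-day window for hearing about it, and the infant follow-up depends on that report. The site will usually learn of a partner's pregnancy only if the subject says so. If his instruction ends when the trial ends, the person who holds the information has no clear prompt to pass it on for most of the window the sponsor set.

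What is at stake is completeness of pregnancy reporting and infant follow-up in a 48-subject Phase 1 trial. No endpoint, analysis set or sample-size figure is involved.

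**Working it through.** **1. Confirm where the trial ends.** The synopsis gives a maximum of 58 days per subject at the minimum washout.

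- Screening and admission, Day -28 to Day -1: 28 days.
- Periods 1 to 3 last 7 days each, so dosing falls on Days 1, 8, 15 and 22.
- Latest follow-up: Day 22 + 8 = Day 30.
- Total: 28 + 30 = 58 days.

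The stated figure reproduces exactly, so the protocol does count the follow-up visit as the end of the trial. Section 5.5 also names the trial and the following 30 days as separate periods, so the one cannot be read to include the other.

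**2. Subjects followed up on schedule.** Gap = 30 minus the post-dose day of follow-up.

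| Follow-up day | Gap (days) | Share of the 30 days |
|---|---|---|
| 6 | 30 - 6 = 24 | 80% |
| 7 | 30 - 7 = 23 | 77% |
| 8 | 30 - 8 = 22 | 73% |

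**3. Withdrawn subjects.** If withdrawal comes w days after the last dose, the trial ends on post-dose day w + 6 to w + 8. The gap is then (22 - w) to (24 - w) days:

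- w = 0: 22 to 24 days
- w = 3: 19 to 21 days
- w = 6: 16 to 18 days
- w = 7 (the morning of the next dose at minimum washout): 15 to 17 days

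**4. Subjects lost to follow-up.** If the final contact attempt falls c days after the last dose, the gap is 30 - c, or zero when c is 30 or more. The documents do not fix c.

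**5. What falls in the gap.** The instruction can be read in two ways.

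- *Reading A: the words date the pregnancy.* A pregnancy arising before follow-up is still to be reported, even if suspected later. Only pregnancies arising between follow-up and day 30 are outside.
- *Reading B: the words date the suspicion or the call.* Anything first suspected after follow-up is outside, including a pregnancy conceived around the Period 4 dose. The section's own example of a sign is a missed or late cycle. Let that sign appear s days after a conception on the Period 4 dosing day; the documents give no value for s. If s is below 6 the pregnancy is inside the instruction, from 6 to 8 it depends on the visit date, and above 8 it is outside.

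The gap is equally long on both readings, but more pregnancies fall outside on B.

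**6. Other provisions.**

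- 5.3 requires the site to report a confirmed partner pregnancy as soon as it is aware. It sets no end date and no relatedness condition, but gives the subject no instruction.
- 5.7.2 monitors immediately reportable events to the last scheduled contact.
- 5.7.3 mentions a telephone contact after the trial period but schedules none, and it covers events judged related to the IMP.
- 5.7.1 provides for a prick test after the last dose, which could bring a later contact. It applies only to subjects with an adverse event of special interest, and its date is not fixed.

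**The case against.** The strongest reply is that subjects take their instructions from the consent process, and the consent form cannot be seen here. Section 5.5 requires that process to cover pregnancy prevention and the follow-up of a reported pregnancy. The protocol is also a translation. Either the form or the original text may already give the 30-day limit. This stands: the documents show a mismatch in the protocol's wording and do not show that subjects were left uninformed.

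A reader might infer that subjects have no instruction at all in the last 22 to 24 days. The documents do not support that. The contraception and sperm-donation rules cover those days. On Reading A, so does the duty to report a pregnancy that arose during the trial.

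A reader might also infer from 5.7.3 that a pregnancy reaching the site after the trial is reported only if judged related to the IMP. Section 5.3 has no such condition, and the notification duty in 5.5 runs to 30 days. Once the site knows, it must report. The open question is only whether the subject is prompted to call.

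The practical weight is small. There are 48 men using two contraceptive methods or abstinence, and Protocol 3.1 gives half-lives of under 3 hours for OPC-61815 and about 14 hours for moxifloxacin. This supports a low priority. It does not explain why one of the four limits in the section differs from the other three.

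**Conclusion.** The mismatch is real and minor. For subjects followed up on schedule, the protocol does not clearly tell the subject to report a partner pregnancy during the last 22 to 24 of the 30 post-dose days (73% to 80%). For subjects withdrawn up to 7 days after a dose, the corresponding gap is 15 to 24 days.

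This rests on two things: taking the trial to end where 3.7.9 says it does, which the 58-day figure confirms, and the consent form not already giving the longer period, which cannot be checked here. It does not mean that the site may ignore a late report, or that any pregnancy would in fact be missed. The QTcF analysis, the assay-sensitivity test and the sample size are unaffected.

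**What to change.** Reword the subject instruction in Protocol 5.5 so that the limit applies to conception and not to the date of suspicion. In substance: subjects are to call the site at once, whenever the suspicion arises, about any partner pregnancy that may have been conceived during the trial or in the 30 days after the last dose of IMP. Check the consent form and align it if it says less.

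Simply adding the 30-day phrase to the present sentence would not be enough. On Reading B, a pregnancy conceived late in the window and suspected after day 30 would still fall outside.

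The cost is one sentence in the protocol and, if needed, one in the consent form. No visit, scheduled call, sample, ECG or analysis is added.

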5.6 Procedure for Breaking the Blind

In the event of an emergency unblinding (knowledge of a subject's treatment is required for the subject's clinical care and safety), the investigator or subinvestigator is to contact the sponsor by phone in order to explain why opening the treatment assignment code is necessary, with both coming to a joint decision if this action is warranted. However, to prevent delays to the investigator, subinvestigator, or medical personnel responding to a potential emergency situation, unblinding of IMP will not be dependent upon the approval from the sponsor (ie, the investigator or subinvestigator will be able to obtain the code breaking information independent of the sponsor). The investigator or subinvestigator must contact the sponsor by telephone or e-mail within 24 hours of opening the code to explain why opening the treatment assignment code was necessary. If the treatment assignment code is unblinded, the sponsor's Clinical Safety and Pharmacovigilance Department must be notified immediately by the investigator or subinvestigator through the IRE reporting process. Documentation of breaking the blind will be recorded in the subject's medical record with the date and time the blind was broken, along with the names of the personnel involved, as well as on the appropriate

pages of the CRF for any AEs leading to the breaking of the blind. Once the blind is broken for a subject, that subject is not allowed to reinitiate treatment with IMP.

5.7 Follow-up of Adverse Events

5.7.1 Follow-up of Nonserious Adverse Events

Nonserious AEs that are identified at any time during the trial must be recorded in the AE column in the CRF, with the current status (ongoing or resolved/recovered) noted. All nonserious events (excluding IREs) that are ongoing at the last scheduled contact will be recorded as ongoing in the CRF. For any AE that has been identified during the course of the trial, additional relevant medical history information may be requested by the sponsor during data analysis to further ascertain causality (including, but not limited to, information such as risk-related behavior, family history and occupation). Follow-up information after the last scheduled contact will be recorded in the subject's medical record.

Based on the results of preceding phase 1 studies, feeling abnormal, feeling hot, erythema, hyperhidrosis, pruritus, rash, urticaria, nausea, epigastric discomfort, and dyspnoea have been selected as AEs of special interest. Because it is suspected that these AEs of special interest will occur, a new formulation with excipients different from those in the previous formulation will be used in this trial. The results of a trial investigating the rate of intravenous administration (263-10-005) also suggest that the AEs of special interest can be decreased by prolonging the duration of administration. However, because the causes of the AEs of special interest are unknown, a prick test will be performed on subjects who experience an AE of special interest in this trial to identify the cause. The investigator, subinvestigator, or designee will perform the prick test after the last dose of IMP (after Period 4 in completed subjects and at an appropriate timing after discontinuation for discontinued subjects) on subjects who experience any AE of special interest during the course of the trial after administration of OPC-61815 at 16 mg, 32 mg, or placebo. The prick test will be performed according to a separately defined procedure. When the investigator or subinvestigator decides that the prick test is unnecessary for a subject experiencing an AE of special interest arising from a clear cause, the reason for the decision will be documented in the source document. The use of anti-histamine drugs is prohibited for 3 days prior to the prick test. Whether a prick test was performed, as well as the date and time, result, and interpretation of the test (if performed), will be documented in the CRF.

5.7.2 Follow-up of Serious Adverse Events and Immediately Reportable Events

In this trial, subjects will be monitored closely for serious AEs and IREs until the end of the trial (last scheduled contact).

Serious AEs and IREs that are identified by or ongoing at the last scheduled contact must be recorded in the AE column in the CRF. If new information related to the SAE or IRE (eg, resolution of the event) was obtained after the last scheduled contact with the subject before the end of the entire trial, the information must be documented in the IRE form and reported to the sponsor and also documented in the AE column in the CRF.

SAEs and IREs must be followed, with any significant follow-up information reported to the sponsor using the IRE form, until the events have resolved or stabilized, or the subject is lost to follow-up or has died. Resolution means that the subject has returned to the baseline state of health, and stabilized means that the investigator or subinvestigator does not expect any further improvement or worsening of the subject's condition.

5.7.3 Follow-up and Reporting of Serious Adverse Events and Immediately Reportable Events Occurring After Last Scheduled Contact

Any new SAEs and IREs that are reported to the investigator or subinvestigator after the last scheduled contact and determined by the investigator or subinvestigator to be related to the use of IMP should be reported to the sponsor. In other words, these events are SAEs and IREs that are identified at the time of follow-up telephone contact or at any other time point after the defined trial period. The investigator or subinvestigator should follow SAEs and IREs identified after the defined trial period and continue to report any significant follow-up information to the sponsor using the IRE form until the events have resolved or stabilized, or the subject is lost to follow-up or has died.

6 Pharmacokinetic/Pharmacodynamic/Pharmacogenomic Analysis

6.1 Pharmacokinetic Analysis Methods

6.1.1 Pharmacokinetic Analysis Set

Pharmacokinetic analysis set includes subjects who are included in the safety analysis set and whose plasma drug concentration was measured.

6.1.2 Pharmacokinetic Analysis

1) Endpoints

- a) Plasma OPC-61815 free form and tolvaptan (OPC-41061) concentrations
- b) PK parameters of plasma OPC-61815 free form and tolvaptan (OPC-41061)
 C_{max} , AUC_{24h} , AUC_t , AUC_{∞} , t_{max} , λ_z , $AUC_{\%Extrap}$, t_{last} , $t_{1/2,z}$, CL^a ,
 CL/BW^a , V_z^a

^aCalculated for OPC-61815 only

2) Statistical analysis method

Descriptive statistics will be calculated in the following manner:

- a) Plasma drug concentration
 - At each blood collection time point, descriptive statistics will be calculated by analyte and treatment.
 - Descriptive statistics to be calculated: Number of subjects, arithmetic mean, standard deviation, coefficient of variation, minimum, median, and maximum.
- b) Plasma pharmacokinetic parameters excluding λ_z , $\lambda_z(\text{lower})$, $\lambda_z(\text{upper})$, $\lambda_z(\text{point})$, and $\lambda_z(\text{Rsqr})$
 - Descriptive statistics will be calculated for each parameter by analyte and treatment.
 - Descriptive statistics to be calculated: Number of subjects, arithmetic mean, standard deviation, coefficient of variation, geometric mean, minimum, median, and maximum.

6.2 Pharmacodynamic Methods

12-lead Holter ECG parameters will be analyzed at a central ECG laboratory. The central laboratory will obtain 3 snapshots for each scheduled ECG from the 12-lead Holter ECG data sent from the trial site, determine the ECG parameters (heart rate, RR interval, PR interval, QRS interval, QT interval, and QTcF interval), and assess waveform patterns. Time windows for data capture are presented in Table 6.2-1. Each data capture will be obtained at an interval of at least 1 minute. The mean from 3 captures will be recorded as the value for each ECG measurement.

Schedule for 12-lead Holter ECG Data Capture^a		Time Window
Day 1	1 hour before IMP administration	Within –5 minutes
	30 minutes before IMP administration	
	15 minutes before IMP administration	
	1 hour after start of IMP administration	Within 5 minutes before end of IMP administration ^b
	1.5 hours after start of IMP administration	Within –5 minutes
	2 hours after start of IMP administration	
	3 hours after start of IMP administration	
	4 hours after start of IMP administration	
	6 hours after start of IMP administration	
12 hours after start of IMP administration		
Day 2	24 hours after start of Day 1 IMP administration	

^a: For moxifloxacin, “IMP administration” instead of “start of IMP administration” in the above table

^b: “Within –5 minutes” for moxifloxacin

6.3 Pharmacokinetic/Pharmacodynamic Methods

For subjects who have QT data and plasma OPC-61815 concentration data after administration of OPC-61815, as well as QT data after placebo administration at the matching time points, differences between OPC-61815 and placebo in change in QTcF interval from baseline at the matching time points are analyzed. A linear mixed-effects model is used, taking plasma OPC-61815 concentration as a fixed effect and subject as a random effect, to investigate the relationships between plasma OPC-61815 concentration and pharmacodynamic parameters.

6.4 Pharmacogenomic Methods

No pharmacogenomic analyses are planned.

7 Statistical Analysis

7.1 Determination of Sample Size

The number of subjects required for central tendency analysis of QTcF, the primary endpoint, was calculated. The number of subjects was calculated to achieve a $\geq 90\%$ probability of the upper limit of the 2-sided 90% CI (1-sided 95% CI) for the time-matched difference in the mean values for the change in QTcF from baseline between the OPC-61815 and placebo values being lower than 10 msec at all time points after administration of each OPC-61815 dose (16 and 32 mg), and a $\geq 90\%$ probability of the lower limit of the 2-sided 98% CI (1-sided 99% CI) for the time-matched difference in

the mean values for the change in QTcF from baseline between the moxifloxacin and placebo values being higher than 0 msec in at least one of the 5 assay sensitivity assessment time points (1, 1.5, 2, 3, and 4 hours) after administration of the positive control moxifloxacin. For the assay sensitivity CI, the increase of type 1 error due to the multiplicity of multiple time points was corrected using the Bonferroni method.

Assuming the within-subject standard deviation to be 7.86, the effect size of moxifloxacin (difference between moxifloxacin and placebo in change from baseline) to be 9.6 msec based on the results of a previous trial (Protocol 331-10-242, a clinical trial of brexpiprazole for evaluation of QT/QTc interval in patients with schizophrenia and schizoaffective disorder), the effect size of OPC-61815 to be 3.0 msec (although no data are available) and the individual time points to be independent, the required number of subjects is 45 for each OPC-61815 dose and 21 for moxifloxacin. Estimating a 5% discontinuation rate, a sample size of 48 subjects was considered necessary.

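### Do the sample sizes of 45 for OPC-61815 and 21 for moxifloxacin contradict the rules they are said to come from?

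*Protocol*

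**What the plan says.** Protocol 7.1 sets two targets, each with a probability of at least 90%.

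- **OPC-61815:** "the upper limit of the 2-sided 90% CI (1-sided 95% CI" for the difference from placebo must be "being lower than 10 msec at all time points after administration of each OPC-61815 dose (16 and 32 mg" respectively. Protocol 7.4.1 lists 8 postdose time points.
- **Moxifloxacin:** the lower limit of a 1-sided 99% interval, Bonferroni-adjusted for five looks, must exceed 0 "in at least one of the 5 assay sensitivity assessment time points (1, 1.5, 2, 3, and 4 hours" after dosing).

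The inputs are given as "Assuming the within-subject standard deviation to be 7.86", a moxifloxacin effect taken "to be 9.6 msec based on the results of a previous trial", and "the effect size of OPC-61815 to be 3.0 msec (although no data are available" at the planning stage). Time points are taken as independent. The result is "the required number of subjects is 45 for each OPC-61815 dose and 21 for moxifloxacin", raised to 48 for 5% discontinuation. The synopsis and SAP section 4 give the same inputs and result. None of the three places names a formula or software.

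**The concern.** One sentence applies one assumption, independent time points, to both results, yet the two results seem to use the time points differently. The figure 45 is labelled as a number for each dose, but it is the threshold for 16 comparisons (2 doses by 8 time points), not 8. The figure 21 is presented as the number for success at one or more of five time points, but it is the threshold for a single time point. On the simplest reading of the moxifloxacin rule the answer is 9, so 21 is more than double what the rule seems to ask for.

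Independence also works in opposite directions. It is cautious when all time points must pass and optimistic when one of several is enough.

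Two things would be at stake. A reader might not be able to verify the sample size from the text, and might take 90% as the power per dose when it is about 95%. If the error ran the other way, the trial could be too small for its primary conclusion or for assay sensitivity.

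**Working it through.** **Inputs.** All are from Protocol 7.1, except the 8 time points, which are from 7.4.1.

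- Within-subject SD 7.86 msec, so the SE of a paired difference is 7.86 × √(2/n).
- OPC-61815: true effect 3.0 and margin 10, so the distance to the margin is 7 msec; 1-sided alpha 0.05.
- Moxifloxacin: true effect 9.6 msec; 1-sided alpha 0.01.

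**Formula.** The power p at one time point is the probability that a noncentral t variable with n − 1 df and noncentrality distance/SE exceeds the 1-sided critical value. The choice of n − 1 df is an assumption. It is the choice that returns both stated figures.

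**Reproducing 45.** At n = 45, SE = 7.86 × √(2/45) = 1.657, noncentrality = 7/1.657 = 4.22 and p = 0.99402.

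| n | p per time point | one dose, p⁸ | both doses, p¹⁶ |
|---|---|---|---|
| 39 | 0.98667 | 89.8% | 80.7% |
| 40 | 0.98832 | 91.0% | 82.9% |
| 44 | 0.99316 | 94.7% | 89.6% |
| 45 | 0.99402 | 95.3% | 90.9% |

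So 45 is the joint number for both doses, and 40 is the number for one dose. The two doses share the placebo data, which p¹⁶ ignores. A simulation with shared placebo gave 91.2% at n = 45 and 89.9% at n = 44, so 45 stands.

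**Does 45 depend on independence?** The Bonferroni bound for all 16 comparisons holds under any correlation: 1 − 16 × (1 − 0.99402) = 90.4% at n = 45, and 1 − 16 × (1 − 0.99316) = 89.1% at n = 44. The figure 45 therefore meets 90% without the independence assumption.

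**Reproducing 21.** At n = 21, SE = 7.86 × √(2/21) = 2.426 and noncentrality = 9.6/2.426 = 3.96. Let p be the power at a time point where the effect is 9.6 msec.

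| n | one time point, p | ≥1 of 5, effect 9.6 at all five: 1 − (1 − p)⁵ | ≥1 of 5, effect 9.6 at one, 0 at four: 1 − (1 − p) × 0.99⁴ |
|---|---|---|---|
| 8 | 36.5% | 89.7% | 39.0% |
| 9 | 43.3% | 94.2% | 45.6% |
| 20 | 89.5% | >99.99% | 89.9% |
| 21 | 91.3% | >99.99% | 91.6% |

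In the last column each null time point passes by chance with probability 0.01. With the stated rule, the stated alpha and independence, 9 is the answer only if the effect is 9.6 msec at all of 1, 1.5, 2, 3 and 4 hours. If it is 9.6 msec at one of them and zero at the rest, the answer is 21. Protocol 7.1 gives one effect size and no time profile, so the text does not choose between the two.

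**Enrolment.** 45/0.95 = 47.4, rounded up to 48. Replacing 21 by 9 leaves this unchanged, because 45 drives it. A strict per-dose 40 would give 40/0.95 = 42.1, rounded up to 43, so the trial as planned is the larger one.

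**The case for a change.** The strongest case for a change is that one standard method returns both 45 and 21 exactly, each at its 90% threshold, and so probably shows what was calculated: 16 comparisons for OPC-61815 and a single time point for moxifloxacin. The wording says neither. With no formula or software named, the wording is all a reader has, and correcting it would cost a few sentences.

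Part of this stands. Attaching 45 to each dose is imprecise if the number was set for both doses jointly, and the text does not say which effect profile lies behind 21. It does not follow that either number is wrong. The target sentence names both doses, so a joint reading is natural, and in a crossover every subject receives each dose. On the per-dose reading, 95.3% still satisfies a floor of 90%. For moxifloxacin, a method that gives 21 under the stated rule exists, so the rule and the number are compatible.

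The worry that independence flatters the one-or-more rule has no force at 21. Power at one time point carrying the 9.6 msec effect, 91.3%, is a lower bound for success at one or more of five, whatever the correlation.

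**Conclusion.** No change follows. Both figures reproduce from the stated inputs: 45 gives 90.9% for both doses jointly and 95.3% for each dose; 21 gives 91.3% at one moxifloxacin time point, and 91.6% under the one-or-more-of-five rule if the other four points show no effect. Each target of at least 90% is met or exceeded on every reading examined, and where a reading would call for fewer subjects (40 or 9) the plan errs towards more. At the 45 completers planned for, single-time-point moxifloxacin power is 99.95%.

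The margin, interval levels, hypotheses, analysis set and model are all specified without reference to these two numbers, so no result or conclusion would change. A statistician who repeats the calculation can recover both numbers, so the gap is one of description.

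This rests on the paired t method with n − 1 df, on 7.86 being the within-subject SD rather than the SD of a difference, and on the planning effects of 3.0 and 9.6 msec. With other df the figures move by only one or two subjects (44 for both doses and 19 for one moxifloxacin time point with crossover-model df), which does not affect the conclusion.
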